#### **C.4. Study Procedures:**

**Educational Intervention group:** The 20 patients randomized to the SLT Educational Intervention group will meet with their ophthalmologist who will discuss both SLT and medication options for treatment of glaucoma, which is currently standard of care. After their eye exam, the patient will meet with the research coordinator. The research coordinator will then ask the patient questions to assess their knowledge, beliefs, barriers, and attitudes about SLT vs. medication as first line treatment of glaucoma (See section D.2.a). The patient will then review the SLT Educational Intervention and be shown the PowerPoint presentation about SLT. After the presentation, the patient will be asked more questions (See section D.2 b). After viewing all information, the Intervention patient will have the opportunity to ask questions to the research coordinator about SLT. If the patient elects to schedule an SLT after the Educational Intervention, they will be assisted with making this appointment.

**Usual Care group procedures:** The 20 patients randomized to the Usual Care group will meet with their ophthalmologist who will recommend both SLT and medication options for treatment of glaucoma, which is currently standard of care. After their eye exam, the patient will meet with the research coordinator who will answer any questions they have about treatment options. The research coordinator will then ask the patient questions to assess their knowledge, beliefs, barriers, and attitudes about SLT vs. medication as first line treatment of glaucoma (See section D.2.a). The Usual Care group will not be exposed to SLT Educational Intervention and will not be asked to watch a video about SLT. If the patient elects to have SLT at any point during the study, we will provide the phone number for them to schedule the procedure. Patients in the Usual Care group will not be assisted with making any SLT appointments.

If patients in either group would like to consult with their ophthalmologist again, we will provide a message to the physician and he/she will call the patient to discuss treatment options again. Doctors will be masked to the group assignment to reduce biasing the outcome. We will track how many patients wanted to speak to their ophthalmologist over the phone or in person in both groups and the outcome of these calls.

**C.5. Tracking Outcomes:** The goal of Aim 1 is to determine if the SLT Educational Intervention used by the research coordinator and physicians with patients could lead to greater utilization of SLT by patients. Rates of SLT will be tracked in each group after patients are asked the first set of questions and after the Intervention group is shown the video. Follow-up eye exam appointments for patients in both groups will be tracked for a 6-month period to

assess the number of patients who elect to have SLT. The rate of SLT will be compared between the SLT Educational Intervention group and the Usual Care group at these time periods.

Patients will provide their name and date of birth on the consent form, both of which will be used to extract and de-identify data from their electronic medical record, including demographics, disease severity, and prior and current glaucoma treatments. Demographic data will include race/ethnicity, gender, and age.

**C.6. Assess Ophthalmologists' Beliefs and Attitudes about Laser (AIM 3):** A total of 15 glaucoma specialists and 20 general ophthalmologists will be interviewed by the research coordinator via telephone or in person. These ophthalmologists will be recruited from the Wills Eye Hospital Glaucoma Service, Wills Eye Hospital Primary Eye Care Service, Wills Eye Medical Staff, community ophthalmologists affiliated with Wills Eye Hospital, and other ophthalmologists as needed. We will recruit these ophthalmologists by asking for their input in helping patients make informed decisions about glaucoma treatment and management and assess how they approach patients with glaucoma.

These ophthalmologists, who will be asked to fill out a survey, will be considered study subjects and will be requested to sign an informed consent form prior to participation. After obtaining informed consent, we will request their input to answer several questions over the phone. Once they agree to participate and complete the phone screening questions, the research coordinator will send them a link to the Powerpoint slides including the video, and request they complete a survey (survey monkey) after viewing the intervention (See Section D.2.c).

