### **C.3. Recruitment and Inclusion Criteria:**

**Patients:** A total of 40 patients will be recruited from the Wills Eye Hospital Glaucoma Care Specialists' private practice and the resident-run Glaucoma Clinic over an 6-month period for this pilot study. Eligible patients will be between 40 and 90 years of age, and have either high-risk ocular hypertension, primary open-angle glaucoma, or pseudo-exfoliation glaucoma with no previous laser trabeculoplasty. Eligible patients will be naive to medication and laser **or** currently being treated with glaucoma eye drop(s). Only patients within three years of a glaucoma-related diagnosis and stable intraocular pressure will be invited to participate.

After IRB approval, the patients' electronic medical records will be reviewed in advance of their next scheduled eye exam. Eligible patients will be invited to participate in the study by letter and/or telephone call, in advance of their scheduled appointment. Eligible patients may also be approached by our study team when checking in on the same day of their eye exam appointment.

All patients will be asked to provide written informed consent, prior to meeting with their ophthalmologist. Once patients are consented, a yellow-colored page with large font (**Patient Enrolled: SLT vs. Meds Study**) will be inserted into the patient's medical chart folder to alert the doctor that the patient is enrolled in the study and that both treatment options should be discussed in detail.

Those enrolled will be randomized to either the SLT Educational Intervention group (n=20) or the Usual Care group (n=20). The knowledge, beliefs, barriers, and attitudes about SLT vs. medication as first line treatment of glaucoma will be assessed in both groups.

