**D.2.a. Questions for Patients in Both Groups after Consenting and Eye Exam**

Are you aware that glaucoma can be treated with laser therapy instead of eye drops?  
Did you know that laser therapy is a possible first option for treating glaucoma before eye drops?  
Did you discuss laser therapy with your glaucoma doctor today?  
Would you consider having laser treatment? Why or why not?  
Would you consider having this laser therapy instead of filling your prescription for eye drops?  
If no, please describe reasons.

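### The coordinator answers treatment questions before the D.2.a survey in Usual Care but after it in the Intervention arm, so the only survey given to both arms is taken under unequal conditions

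*Combined protocol and SAP*

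**What the plan says.** C.3 places consent before the consultation: "All patients will be asked to provide written informed consent, prior to meeting with their ophthalmologist". It then says that enrolled patients are randomised 20 to each arm, without saying when in the visit this happens.

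C.4 describes each arm as already randomised when it reaches the doctor: "The 20 patients randomized to the SLT Educational Intervention group will meet with their ophthalmologist who will discuss both SLT and medication options" for the Intervention arm and "The 20 patients randomized to the Usual Care group will meet with their ophthalmologist who will recommend both SLT and medication options" for Usual Care. After the exam the two paths differ.

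- **Intervention:** the coordinator asks D.2.a. Next, "The patient will then review the SLT Educational Intervention and be shown the PowerPoint presentation about SLT". D.2.b follows, and then time for questions.
- **Usual Care:** "After their eye exam, the patient will meet with the research coordinator who will answer any questions they have about treatment options". D.2.a comes after that.

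D.2.a is headed "Questions for Patients in Both Groups after Consenting and Eye Exam". Its items ask whether the patient knows that laser can replace drops or come before them, whether laser was discussed that day, and whether the patient would consider it, with reasons. D.2.b is asked only in the Intervention arm.

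C.5 and D.1.a track SLT rates after the first set of questions, after the video and over six months of follow-up. C.5 says the arms are compared at these times. D.1.a makes completed SLT the primary outcome and places patients' beliefs and attitudes in the secondary outcome. Section F applies Fisher's exact test to pre- and post-intervention survey answers. C.4 says doctors are masked to the arm; no masking of the coordinator is described.

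**The concern.** D.2.a measures awareness of laser treatment and willingness to have it. A coordinator who has just answered a patient's treatment questions may have supplied the awareness that the next question measures. As written, this can happen before D.2.a in Usual Care only.

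The coordinator's script differs by arm from the start of the meeting, so the person asking open questions about reasons already knows the allocation. Nothing in the design needs this: the first step that has to differ by arm is the presentation, which comes after D.2.a.

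At stake are a comparison of the arms on the survey and the early SLT time point. The trial's main comparison is not at stake.

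**Working it through.** The plan gives no figure to reproduce on this point, so the check is mainly one of sequence.

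**Order of events, from C.3, C.4 and D.2**

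| Step | Intervention | Usual Care |
|---|---|---|
| 1 | Consent | Consent |
| 2 | Eye exam, both options raised | Eye exam, both options raised |
| 3 | D.2.a | Coordinator answers treatment questions |
| 4 | Presentation and video | D.2.a |
| 5 | D.2.b | – |
| 6 | Coordinator question time | – |

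The arms diverge at step 3, so the allocation must be known by then. The wording of C.4 implies that it is known before step 2, but no section says so. The argument does not depend on which is true.

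**Which uses of the data are affected**

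- *Between-arm reading of D.2.a:* affected. It sets Usual Care answers given after coordinator question time against Intervention answers given before it.
- *Pre/post comparison in section F:* not affected by the order if the pre answers come from Intervention patients only, because D.2.a there directly precedes the presentation. Section F does not say this. If Usual Care answers are pooled in, the problem enters.
- *SLT rate after the first set of questions (C.5, D.1.a):* affected. At that moment Usual Care has had coordinator question time and Intervention has not.
- *Completed SLT over the whole study:* the randomised comparison stands.

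**Size**

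Input: 20 patients per arm (C.3). The number of answers changed by prior question time, k, is not given and is assumed.

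Shift in an item within one arm = k/20:

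- k = 1: 1/20 = 5 points
- k = 2: 2/20 = 10 points
- k = 3: 3/20 = 15 points
- k = 4: 4/20 = 20 points

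If all 40 patients' answers were pooled as pre answers, the shift would be k/40, so 1/40 = 2.5 points and 3/40 = 7.5 points.

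**Would the data reveal it?** The table gives the exact power of a two-sided Fisher test at 0.05 with 20 per arm. The item rates and the 0.05 level are assumed, since the plan states neither.

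| Assumed rates | Shift | Power |
|---|---|---|
| 30% vs 40% | 10 points | 0.06 |
| 30% vs 50% | 20 points | 0.16 |
| 50% vs 90% | 40 points | 0.74 |

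A shift of 10 or 20 points would probably pass unnoticed.

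**The case against.** The best case for the plan is that little depends on this order. Section F tests only pre- against post-intervention answers, and D.2.b exists only in the Intervention arm. No between-arm test of D.2.a is planned, and the order used in Usual Care cannot disturb a comparison made within the other arm. If someone did compare the arms, answering questions first would probably raise awareness in Usual Care and so make an education effect look smaller. The primary outcome does not use the survey. All of this stands, except that C.5 does compare SLT rates between arms at the early time point and section F leaves the source of its pre answers open.

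Several stronger readings are tempting but not supported:

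- **Patients are randomised before the exam.** This is the natural reading of C.4, but the phrase could simply be a label opening each arm's description. What can be said is that the time is not stated.
- **D.2.a is a failed baseline.** The plan never calls it a baseline. It is meant to follow the consultation, since one item asks about that day's discussion. Being asked after randomisation does not by itself bias it.
- **Doctors treat the arms differently.** One arm's text says *discuss*, while the other reads "who will recommend both SLT and medication options for treatment of glaucoma". This is probably loose drafting: the doctors are masked, and the yellow chart page in C.3 gives the same cue for every enrolled patient. The two wordings should still be reconciled.
- **Early allocation unmasks doctors or causes arm-dependent dropout.** The yellow page marks enrolment and not the arm, and the documents show no route to either event.

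**Conclusion.** The concern holds in a limited form, at minor severity. C.4 sets a different coordinator order in each arm, so D.2.a is taken under unequal conditions by someone who must already know the allocation. This weakens any between-arm reading of D.2.a, any pooled pre answers and the early SLT comparison.

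The amount of bias cannot be derived from the documents. The 5 points per changed answer is arithmetic on 20 patients; how many answers would change is an assumption. The conclusion also assumes that C.4 will be followed in the order written. A reader should not infer that the within-arm pre/post comparison or the primary comparison of completed SLT is invalid on this ground.

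**What to change.** In C.3 and C.4, write one sequence for all 40 patients:

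1. Consent.
2. Eye exam, described in identical words for both arms.
3. D.2.a.
4. The coordinator opens the next concealed assignment.
5. Intervention: presentation, D.2.b, then question time. Usual Care: question time.

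This states the time of randomisation, keeps the coordinator unaware of the arm while asking D.2.a, and puts question time after D.2.a for everyone. It makes D.2.a comparable between arms and removes the imbalance in coordinator contact at the first SLT time point.

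The cost is a protocol edit and sealed or electronic assignments opened later in the same visit. It needs no extra staff, visits or patients.

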**C. Research Design and Methods:**

**C.1. Human Subjects and Informed Consent:** The study involves human subjects, all of whom will give informed consent prior to enrollment. The study will seek approval from Wills Eye Hospital's Institutional Review Board, and will be conducted in accordance with the Health Insurance Portability and Accountability Act. Study procedures will adhere to the Declaration of Helsinki for research involving human subjects.

**C.2. Development of the SLT Educational Intervention (AIM 1):** The Educational Intervention about SLT as first line therapy to treat glaucoma will be developed by the principal investigator, co-investigators, the research coordinator, and research assistants using the American Academy of Ophthalmology Practice Pattern Guidelines, and the Glaucoma Research Foundation resources. The intervention will be developed with the aim of improving patients' understanding of what laser treatment is, what are the benefits, and why it should be strongly considered as a first-line treatment for glaucoma before any medications. We will adapt the content from the Glaucoma Research Foundation web page as well as the material in the *Understanding and Living with Glaucoma* booklet ([www.glaucoma.org/treatment/laser-surgery.php](http://www.glaucoma.org/treatment/laser-surgery.php)).

Once the laser procedure is described alongside images and text written at the 4th grade reading level, a MS Powerpoint presentation will be developed, in consultation with a small group of patients (n=5) who have elected to have a laser procedure in at least one eye to treat glaucoma. We will share the Educational Intervention with these patients before and after they have the SLT procedure, and ask them to assist us in providing culturally and linguistically appropriate terms and language to describe the procedure.

We will also ask them to help us develop the "frequently asked questions" section including the answers that they feel would be most helpful to advocate for SLT as first line therapy for glaucoma. We will base these responses on the Glaucoma Research Foundation's web site intervention ([www.glaucoma.org/treatment/selective-laser-trabeculoplasty-10-commonly-asked-questions.php](http://www.glaucoma.org/treatment/selective-laser-trabeculoplasty-10-commonly-asked-questions.php)).

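### Unscripted answers from the research coordinator in Usual Care leave the contrast between arms open to contamination, and put D.2.a on an unequal footing

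*Combined protocol and SAP*

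**What the plan says.** In C.4, a Usual Care patient first sees the ophthalmologist, who covers both SLT and medication; the protocol describes this as standard of care. Then "the patient will meet with the research coordinator who will answer any questions they have about treatment options". The D.2.a questions follow. The same paragraph states that "The Usual Care group will not be exposed to SLT Educational Intervention and will not be asked to watch a video about SLT".

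The coordinator is not neutral with respect to the programme. Under C.2 it "will be developed by the principal investigator, co-investigators, the research coordinator, and research assistants", and it includes a frequently-asked-questions section whose content is to be shaped by patients choosing "answers that they feel would be most helpful to advocate for SLT as first line therapy for glaucoma". C.5 describes the "SLT Educational Intervention used by the research coordinator and physicians with patients".

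In the Intervention arm the order differs: eye exam, D.2.a, presentation and video, further questions (D.2.b), and then "the Intervention patient will have the opportunity to ask questions to the research coordinator about SLT".

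On masking, C.4 says only that "Doctors will be masked to the group assignment to reduce biasing the outcome". The documents describe no script, content limit, separate staff member or log for the coordinator's answers.

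**The concern.** The trial asks whether a clearer explanation of SLT raises uptake. In Usual Care, an open question session is run by someone who helped write that explanation and who uses it in the other arm. A control patient who asks about laser is an obvious occasion for the FAQ content to be repeated aloud. The session is a study procedure that comes after the consultation the protocol calls standard of care, so it is not clear that it represents usual care at all.

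The primary outcome, completed SLT compared between arms, is at stake. Leaked content would raise uptake in Usual Care and pull the difference towards zero. How much leaks would depend on who asks and how the coordinator replies, and nothing recorded under the plan would allow it to be estimated or adjusted for.

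The secondary outcome on patients' knowledge and attitudes is affected too, because controls have had a question session before D.2.a and Intervention patients have not.

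**Working it through.** **Step 1: the coordinator's contact in each arm (C.4).**

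| | Usual Care | Intervention |
|---|---|---|
| Ophthalmologist discusses SLT and medication | yes | yes |
| Coordinator Q&A before D.2.a | yes, any treatment question | none described |
| D.2.a questions | yes | yes |
| Presentation and video | no | yes |
| Coordinator Q&A after the programme | not applicable | yes, about SLT |
| Help booking SLT | no, phone number only | yes |
| Limit on, or log of, coordinator answers | none stated | none stated |

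Two things follow. First, both arms have Q&A, but the sessions are not matched. Intervention patients ask after the programme content has been delivered, whereas for a control any programme content in an answer is new exposure. Second, D.2.a follows Q&A in one arm only. Several of its items ask about awareness of laser and willingness to consider it, which a question session could change.

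**Step 2: size, as an illustration.** The plan has no power figure to reproduce. From the documents: 20 patients per arm (C.3). Assumed, because the documents do not give them: SLT rates p0 (Usual Care) and p1 (Intervention), two-sided alpha 0.05, and Fisher's exact test for the primary comparison (section F names that test only for survey answers).

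Let c be the share of the intervention effect that reaches Usual Care through the coordinator's answers, averaged over all controls. Then

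- diluted Usual Care rate = p0 + c(p1 − p0)
- remaining difference = (1 − c)(p1 − p0)

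For example, with p0 = 10%, p1 = 40% and c = 20%, the Usual Care rate is 10 + 0.20 × 30 = 16% and the difference is 0.80 × 30 = 24 points.

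Power is the sum of the binomial probabilities of all 21 × 21 possible outcome pairs for which Fisher's p is at most 0.05.

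| c | 10% vs 40%: difference (points) | power | 10% vs 50%: difference (points) | power |
|---|---|---|---|---|
| 0 | 30 | 49% | 40 | 74% |
| 10% | 27 | 38% | 36 | 61% |
| 20% | 24 | 29% | 32 | 47% |
| 30% | 21 | 21% | 28 | 35% |
| 50% | 15 | 11% | 20 | 16% |

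Other assumed pairs behave in the same way. Power at c = 0, 10%, 25% and 50% is 45%, 33%, 21% and 9% for 5% vs 30%, and 65%, 52%, 35% and 14% for 20% vs 60%.

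**Step 3: how to read c.** It is a share of effect, not a share of patients who hear something. The two coincide only if every exposed control receives the full effect. A spoken answer brings no slides, video or booking help, so the table's larger values of c are upper-end cases.

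**The case against.** A reader might infer that the plan contradicts itself. It does not. The exclusion covers a defined product (text and images, slides, FAQ section, embedded video), and answering a question delivers neither that product nor the video. What stands is that the purpose of the exclusion is left unprotected.

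A reader might also infer that the contrast is certain to be diluted. The documents do not support that either. The coordinator must know the arm, because the procedures differ by arm, and could be less encouraging to controls, which would widen the difference. Dilution is the main risk, not an established fact.

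The effect may also be small. Both arms have already heard about SLT from the ophthalmologist, and spoken answers cannot carry the whole package. This is fair, and it is why the power figures are illustrative.

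Finally, the study is a 40-patient pilot. At 10% vs 40%, power is only 49% with no leakage, so a null result would be weak evidence in any case. It would be wrong to attribute that mainly to the coordinator's session. Still, completed SLT compared between arms is the stated primary outcome, and a design this small has little contrast to spare.

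**Conclusion.** The point holds as an uncontrolled risk of contamination and performance bias, created by a procedure the plan positively specifies. Followed as written, C.4 can pass part of the tested content to controls, and nothing recorded would show whether it did.

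Its size cannot be obtained from the documents. Under the assumptions above, a transfer of 10% of the effect costs about 11 percentage points of power at 10% vs 40% (49% to 38%) and about 13 at 10% vs 50% (74% to 61%). The losses at 30% or 50% transfer are upper-end. None of these figures describes a bias that widens the difference, which is also possible.

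The order of D.2.a does not depend on any assumed rate. As described, its answers are not comparable between arms. The before-and-after comparison within the Intervention arm is not affected by this.

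**What to change.** Amend C.4 as follows:

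1. Ask D.2.a before any coordinator Q&A in both arms.
2. In Usual Care, limit the coordinator's answers to one fixed, neutral sheet on treatment options that contains no programme content. Pass further questions to the ophthalmologist by the message and call-back route C.4 already provides.
3. Keep the post-presentation Q&A in the Intervention arm and describe it as part of the intervention. Sending those questions to the doctors instead would change what is being tested and could reveal allocation to doctors who are meant to be masked.
4. Log the questions put to the coordinator and the answers given in both arms, and report them with the primary result.

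The cost is one sheet to prepare, a short log, and a few more call-backs for doctors. C.4 also tracks requests to speak to the doctor again; since the sheet would send more Usual Care patients down that route, those counts should be interpreted with this in mind.

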## **D.1 Data Management and Analysis**

**D.1.a. Assessment Measures:** The primary outcome measure is the number of patients who complete an SLT over the study period. Rates of SLT procedures will be compared between patients enrolled in the SLT Educational Intervention group versus the Usual Care group. Rates of SLT will be tracked in each group after patients are asked the first set of questions and after the Intervention group is shown the video. Follow-up eye exam appointments for patients in both groups will be tracked for a 6-month period to assess the number of patients who elect to have SLT.

The secondary outcome is to assess the beliefs and attitudes of patients and a group of ophthalmologists about SLT as first line therapy before and after viewing Educational Intervention. The research coordinator will ask all patients questions about their knowledge, beliefs, barriers, and attitudes about SLT vs. medication as first line treatment of glaucoma. These questions will be developed with [name], a psychologist and vision researcher at Sidney Kimmel Medical College with extensive experience in survey development and sampling techniques. She will be consulted during the development phase to revise and implement the following questions. If a more understandable explanation of the risks/benefits of SLT versus medications results in a significant increase in SLT treatments, that suggests that the real barrier is patient understanding and perhaps to a lesser extent physician education.

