**D.2.b. Questions for Intervention Patients After Viewing the Presentation and Video**

Did you have any questions about the educational program we showed you?  
Would you consider having laser therapy to treat your glaucoma?  
Would you consider having this laser therapy instead of filling your prescription for eye drops?  
If no or maybe, let's discuss why?  
If yes, can I help you to schedule a laser appointment at your convenience?

In order to assess the beliefs and attitudes of a group of ophthalmologists about SLT as first line therapy before and after viewing Educational Intervention, we will ask the following questions to determine how they approach newly diagnosed patients with glaucoma.

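### Help with booking SLT goes to the Educational Intervention arm only, so a difference in completed SLT is a package effect that may come partly from easier booking

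*Combined protocol and SAP*

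**What the plan says.** - **Intervention arm, C.4:** "If the patient elects to schedule an SLT after the Educational Intervention, they will be assisted with making this appointment".
- **Intervention arm, D.2.b** (asked of this arm only, after the video): the list asks "Would you consider having this laser therapy instead of filling your prescription for eye drops", then prompts "If no or maybe, let's discuss why", and ends "If yes, can I help you to schedule a laser appointment at your convenience".
- **Usual Care arm, C.4:** for a patient who chooses SLT, "we will provide the phone number for them to schedule the procedure". The next sentence is "Patients in the Usual Care group will not be assisted with making any SLT appointments".
- **Primary outcome, D.1.a:** "The primary outcome measure is the number of patients who complete an SLT over the study period". C.5 and D.1.a also say that the number of patients choosing SLT will be tracked in both arms over 6 months.
- **Interpretation, D.1.a:** if a clearer account of risks and benefits leads to significantly more SLT, "that suggests that the real barrier is patient understanding and perhaps to a lesser extent physician education".
- **What the intervention is:** AIM 1 and C.2 describe information, namely slides, a video and frequently asked questions. Neither mentions booking. AIM 2 measures the intervention's effectiveness by conversions to SLT. The Hypothesis concerns better informed patients and ophthalmologists.
- **Analysis, Section F:** Fisher's exact test is named for survey answers before and after the intervention. No test is named for SLT rates.

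**The concern.** A patient reaches the primary outcome by deciding on SLT, booking it and having it done. Education is meant to act on the decision. Booking help acts on the next step, and only one arm gets it. It can therefore raise completion in the Intervention arm even if both arms understand SLT equally well and choose it equally often.

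What is at stake is attribution. This is a 40-patient pilot whose use is to inform later work. If an increase is credited to patient understanding when part of it came from easier booking, the next study may be built around the wrong component.

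**Working it through.** **Does anything in the plan separate the two routes?**

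1. *Tracking of patients who choose SLT (C.5, D.1.a).* Choosing comes before completing, so this is the closest candidate. But the plan does not define choosing separately from completing, and does not say it is recorded before booking help is given.
2. *The survey item on laser instead of drops.* It appears in D.2.a (both arms) and again in D.2.b, where it precedes the scheduling offer. However, being willing to consider SLT is weaker than choosing it, the before-and-after change in the Intervention arm has no control, and Section F plans no between-arm comparison of the item.
3. *Masking of doctors (C.4).* This does not touch help given by the coordinator.

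So nothing in the plan separates them as written.

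**How large could the effect of booking help be?** The documents give no choice or completion rates, so there is no planned figure to reproduce and every rate below is assumed.

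- Arm size: 20 and 20 (C.3).
- *e* = share choosing SLT, the same in both arms (no educational effect): 10% to 70%.
- Completion among those who choose it: 90% with booking help; *c* = 50%, 60%, 75% or 85% with the phone number only.
- Test: two-sided Fisher, significant if p ≤ 0.05. This too is an assumption for SLT rates.

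Completed rate = *e* × 0.90 in the Intervention arm and *e* × *c* in Usual Care, so the difference is *e* × (0.90 − *c*). The chance of significance comes from summing the binomial probabilities of all outcome pairs that the test rejects.

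Each cell gives the difference in percentage points, then the chance of a significant result:

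| *e* | *c* = 50% | *c* = 60% | *c* = 75% | *c* = 85% | Equal help (90% in both arms) |
|---|---|---|---|---|---|
| 10% | 4.0; 1.1% | 3.0; 1.0% | 1.5; 0.9% | 0.5; 0.9% | 0; 1.0% |
| 20% | 8.0; 5.2% | 6.0; 3.7% | 3.0; 2.5% | 1.0; 2.2% | 0; 2.2% |
| 30% | 12.0; 8.7% | 9.0; 5.6% | 4.5; 3.1% | 1.5; 2.5% | 0; 2.4% |
| 50% | 20.0; 17.9% | 15.0; 10.1% | 7.5; 3.9% | 2.5; 2.4% | 0; 2.2% |
| 70% | 28.0; 29.1% | 21.0; 16.0% | 10.5; 5.5% | 3.5; 2.8% | 0; 2.5% |

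Example: *e* = 50% and *c* = 60% give 0.50 × 0.90 = 45% against 0.50 × 0.60 = 30%, a difference of 15 points. The chance of significance is 10.1%, against 2.2% with equal help.

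The chance is below 5% in 12 of the 20 unequal-help cells and at least 10% in 4. Those 4 all need at least 50% choosing SLT and at most 60% completing unaided.

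**The case against.** The strongest reply is that this is a pragmatic pilot whose package is disclosed in advance. C.4 places booking help under the Educational Intervention group and D.2.b scripts it. Usual Care patients who choose SLT get the number, can ask for another call from their ophthalmologist, and are followed for 6 months, so booking help may matter little. This stands as far as it goes: the comparison of packages is valid and the effect may be negligible. What is missing is a description in C.2 and AIM 2 that matches what is delivered, or an interpretation limited to it.

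Three stronger readings are tempting and should be resisted.

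- *That D.1.a credits any increase to understanding.* It does not. Its inference is conditional on the clearer explanation having produced the increase. The fair criticism is that the design cannot show this.
- *That only the Intervention arm gets to talk through its doubts.* In C.4 the coordinator also answers Usual Care patients' questions about treatment options, and D.2.a asks both arms for reasons for or against laser. The post-video prompt is extra contact, but a minor point, and may fairly count as education.
- *That the trial could say nothing about understanding even with equal booking.* Equal booking removes this particular alternative explanation, and the argument here goes no further.

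**Conclusion.** The point holds as a matter of attribution. The asymmetry is explicit, it lies on the path to the primary endpoint, and it favours the Intervention arm. A higher completed-SLT rate would be evidence for education plus booking help. It would not show that the explanation was the cause.

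That conclusion needs none of the assumed rates. The size does: from negligible (0.5 points) to substantial (28 points), with most combinations giving little extra chance of a significant result. The table shows what is possible and does not estimate what will happen. A reader might infer that the randomised comparison is invalid or that a positive result would be spurious. The documents support neither. This should be fixed before enrolment, but it does not undermine the trial.

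**What to change.** 1. **Use one booking rule in both arms (C.4 and D.2.b).** Give either the same help on request or the phone number only. Delete the sentence withholding help from Usual Care, and use the D.2.b scheduling offer in both arms or in neither. *Cost:* the between-arm difference may be smaller. Help in both arms makes the comparator slightly more supportive than usual care, and the phone number alone may lower uptake in the Intervention arm.

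   *If the asymmetry is kept,* name booking help as part of the intervention in C.2 and AIM 2, and limit D.1.a to an effect of education plus booking help, not of patient understanding alone. *Cost:* wording only, but the effect of education alone on completed SLT stays unestimated.

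2. **Define the decision and record it before booking (C.5).** Record choosing SLT as yes / undecided / no in both arms, at the end of the coordinator meeting and before any booking step. In Section F, report the between-arm difference with a 95% CI, descriptively, alongside completed SLT, which stays primary. *Cost:* one question at a meeting both arms already have. *Limit:* precision is low. With 10/20 against 6/20 saying yes, the difference is 20 points with a Newcombe 95% CI of about −10 to +45, so this describes where the arms diverge and cannot settle the question alone.
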